5.1. Inclusion Criteria

Subjects are eligible to be included in the study only if all of the following criteria apply:

Age and Gender

1. Subjects must be 21 to 75 years of age inclusive, at the time of signing the informed consent form (ICF).
2. Male or female.

Type of Subject and Disease Characteristics

3. Biopsy-confirmed NASH with fibrosis stage F2, or F3 per NASH CRN system and NAS ≥ 4 , with a score of at least 1 in each of steatosis, ballooning degeneration, and lobular inflammation, either through a historical biopsy or a biopsy at screening. A historical biopsy should be obtained within 6 months prior to first day of Screening (i.e., day ICF is signed) that is deemed suitable for interpretation by a central reader if the subject had no significant change in metabolic status (control of diabetes, hyperlipidemia or $>5\%$ weight loss or gain).

Pregnancy and Contraception

Contraceptive use by men or women should be consistent with local regulations regarding the methods of contraception for those participating in clinical studies. Refer to Appendix 4 (Section 10.4) for definitions of women of childbearing potential (WOCBP) and contraception guidance.

4. All subjects (male or female) who are of childbearing potential must agree to use highly effective, double contraception (both male and female partners) during the study. Use of a condom with spermicide in a male subject who underwent vasectomy is also acceptable as double contraception. Use of highly effective, double contraception must continue for 30 days after the last dose of IP. Female subjects should not donate oocytes during this time. Male subjects must not donate sperm during this time. Rhythm methods are not considered as highly effective methods of birth control. Subject abstinence for the duration of the study and 30 days after the last dose of IP is acceptable if it is the subject's regular practice.
5. Females of childbearing potential must have a negative serum pregnancy test at Screening and a negative urine pregnancy test on Day 1. Females of childbearing

potential must agree to undergo a pregnancy test prior to dosing at the timepoints specified in the SoA.

6. Sexually active male subjects whose female partner is pregnant must agree to use a condom.

Informed Consent and Study Requirements

7. Capable of giving signed informed consent, which includes compliance with the requirements and restrictions listed in the ICF and in this protocol.

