- Repeating liver enzymes, serum bilirubin, hematology panel (for eosinophil count), and INR tests two or three times weekly. Frequency of repeat testing can decrease to once a week or less if abnormalities stabilize or the IP has been discontinued and the subject is asymptomatic.
- Obtaining a more detailed history of symptoms and prior or concurrent diseases.
- Obtaining a history of concomitant drug use (including nonprescription medications and herbal and dietary supplement preparations), alcohol use, recreational drug use, and special diets.
- Ruling out acute viral hepatitis types A, B, C, D, and E; autoimmune or alcoholic hepatitis; hypoxic/ischemic hepatopathy; and biliary tract disease.
- Obtaining a history of exposure to environmental chemical agents.
- Obtaining additional tests to evaluate liver function, as appropriate (e.g., INR, direct bilirubin).
- Considering gastroenterology or hepatology consultations.

Note: If a visit to the clinic is not feasible, laboratory testing can be performed by home health and sent to the central laboratory, or locally and the results should be promptly communicated to the Investigator site.

7.1.2. Monitoring and Study Continuation of Subjects with NASH Fibrosis Stage F1 or F4

The initial protocol allowed subjects to be included based on the biopsy read by one of the 2 expert pathologists. Version 3 Amendment #2 (March 11, 2022) changed the biopsy reading methodology to a central panel of 3 independent pathologists. This change in methodology

resulted in a change in fibrosis stage at baseline for some subjects (from F2 or F3 to either F1 or F4). These subjects and subjects evaluated as F4 during the study will be managed as follows:

1. Subjects with baseline fibrosis stage F1 as determined by a consensus of 3 central pathologists may continue all phases of the study and will be analyzed separately as an exploratory population.
2. Subjects with baseline fibrosis stage F4 (cirrhotic) as determined by a consensus panel of 3 central pathologists (as described above) will participate in all phases of the study as an exploratory population and will be analyzed separately provided:
 - a. Their liver disease is considered well compensated as assessed by Child-Pugh Class A criteria (See Section 10.8), and
 - b. There is no evidence of hepatic decompensation (i.e., hepatic encephalopathy, ascites, or bleeding varices) as assessed by the PI according to usual standard of care, and

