4.1.2. Key Secondary Efficacy Endpoints

- [c] Proportion of patients with at least a 2-point improvement in NAS and no worsening of fibrosis at Week 24 compared to baseline
- [d] Proportion of patients with NASH resolution AND fibrosis improvement ≥ 1 stage at Week 24 compared to baseline.
- [e] Proportion of subjects with ≥ 2 -point improvement in NAS score AND are MRI-PDFF responders⁵ AND ALT responders⁶ at Week 24 compared to baseline.

[Table 2](#) is a summary of meeting selected criteria for each primary and key secondary efficacy endpoint.

Table 2: Primary and Key Secondary Endpoints Criteria

Criteria (at Week 24)	[a]	[b]	[c]	[d]	[e]
NASH resolution	Y			Y	
No NASH worsening		Y			
No fibrosis worsening	Y		Y		
Fibrosis ≥ 1 stage improvement		Y		Y	
≥ 2 points NAS improvement			Y		Y
MRI-PDFF responder					Y
ALT responder					Y

² Resolution of NASH includes the total absence of ballooning (score=0) and absent or mild inflammation (score 0 to 1).

³ Worsening of fibrosis is defined as progression of fibrosis ≥ 1 stage.

⁴ Worsening of NASH is defined as increase in NAS for ballooning, inflammation, or steatosis.

⁵ $\geq 30\%$ reduction from baseline in liver fat by MRI-PDFF.

⁶ ≥ 17 U/L or $\geq 30\%$ reduction from baseline in ALT.

Efficacy Assessments: NAS Score and NASH CRN Fibrosis Staging

The NASH CRN semi-quantitative scoring of histological features (steatosis, ballooning degeneration, and lobular inflammation) which together comprise the unweighted sum to produce the NAFLD Activity Score (NAS) and the NASH CRN Fibrosis staging system are as follows:

	Steatosis	Ballooning	Lobular Inflammation
Grade 0	$\leq 5\%$	None	No foci
Grade 1	$>5\% \text{ and } \leq 33\%$	Few Balloon cells	$<2 \text{ foci}/200x$
Grade 2	$>33\% \text{ and } \leq 66\%$	Many cells/prominent ballooning	$2-4 \text{ foci}/200x$
Grade 3	$>66\%$		$>4 \text{ foci}/200x$

NAS total score ranges from 0 – 8, which is the sum of Steatosis, Ballooning, and Lobular Inflammation.

Stage (Score)	Fibrosis
Stage 0 (0)	None
Stage 1 (1)	Perisinusoidal or periportal
Stage 1A (1)	Mild, zone 3, perisinusoidal
Stage 1B (1)	Moderate, zone 3, perisinusoidal
Stage 1C (1)	Portal/periportal
Stage 2 (2)	Perisinusoidal and portal/periportal
Stage 3 (3)	Bridging fibrosis
Stage 4 (4)	Cirrhosis

NASH CRN fibrosis stage ranges from F0 (without fibrosis) to F4 (cirrhosis) per NASH CRN system.

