6. ANALYSIS POPULATIONS

For purposes of analysis, the following populations are defined:

Population	Description
Randomized Analysis Set	All enrolled subjects who are assigned a randomization number in the study.
Full Analysis Set (FAS)	All enrolled subjects with confirmed fibrosis stage F2 or F3 and NAS ≥ 4 at baseline per independent review by a 3-pathologist panel who are eligible and assigned a randomization number in the study and received at least 1 dose of IP. For analysis purposes, subjects will be analyzed according to the treatment they were randomized to regardless of actual treatment received.
Safety Analysis Set	All randomized subjects who receive at least 1 dose of IP. In this population, subjects will be summarized based upon the IP actually received, regardless of the IP to which they were randomized.
PK Analysis Set	All subjects in the FAS who have sufficient data to adequately characterize the trough serum pegozafermin concentrations and have no other events or protocol violations that would adversely affect results, such as not completing the full dose. The analysis population for any population PK modeling may be defined separately in a population PK data analysis plan.
MRI-PDFF Analysis Set	All subjects in the Full Analysis Set who have a baseline and at least one follow up MRI-PDFF assessment.

Primary Analysis

- Patient dispositions and screen failure summary will be presented for all subjects screened.
- Baseline characteristics, protocol deviations, medical histories and concomitant medications will be assessed for Randomized Analysis Set.
- All primary, secondary, and exploratory efficacy endpoints of Main Study will be assessed for Full Analysis Set.
- Exposure and safety assessments will be analyzed based on Safety Analysis Set.
- PK endpoints will be displayed and analyzed for all subjects with applicable data in the PK Analysis Set.

Final Analysis

- Protocol deviations and concomitant medications will be summarized based on Randomized Analysis Set including data in Extension Study.
- Exposure and safety assessments will be summarized based on Safety Analysis Set including data in Extension Study.
- PK endpoints will be displayed and analyzed for all subjects with applicable data in the PK Analysis Set.

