7.8. Efficacy Analysis for Main Study

The primary efficacy endpoints are (1) proportion of subjects with NASH resolution without worsening of fibrosis at Week 24 compared to baseline (2) proportion of subjects achieving improvement of fibrosis ≥ 1 stage without worsening of NASH at Week 24 compared to baseline. The following hypothesis will be tested for each primary endpoint:

- The null hypothesis: there is no difference in the proportion of subjects meeting the primary endpoint between the placebo and each pegozafermin dose group.
- The alternative hypothesis: the proportion of subjects meeting the primary endpoint between the placebo and each pegozafermin dose group is different.

The study will be considered successful if a given pegozafermin dose group is demonstrated to be superior to the placebo group in either of the two primary endpoints at 0.05 significance level.

Estimand Framework

As detailed in the ICH E9 (R1) addendum, the following five attributes will define the estimand framework in this trial. The primary estimand will be defined as a treatment policy (TP) estimand, which compares treatment outcomes in two randomized arms at 24 weeks post-randomization irrespective of what changes in treatment could have occurred post-randomization as a result of various intercurrent events (ICE). To implement TP strategy, it will be important that outcomes are collected and recorded after occurrence of ICE's as close to the 24 week time point, regardless of what actual treatment the patient may be receiving. Below are the 5 attributes of the primary estimand:

- Treatment conditions: Randomization to Pegozafermin (15 mg QW or 30 mg QW or 44 mg Q2W) or Placebo, regardless of ICE's and deviations from the randomized treatment and actual treatment received during or at the end of the treatment period.
- Population: Randomized subjects with fibrosis stage 2 or 3 and NAS ≥ 4 at baseline per 3-panel consensus read who received at least 1 dose of IP.
- Endpoints: NASH resolution without worsening of fibrosis at Week 24 compared to baseline; improvement of fibrosis ≥ 1 stage without worsening of NASH at Week 24 compared to baseline
- Intercurrent events (ICEs): Three types of ICEs are defined below.
- Population-level summary: Between treatment group difference expressed in terms of the percentage differences in achieving the endpoints.

The following types of ICEs will be documented in course of the study.

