7.8.1.2.3. Inclusion of subjects randomized but deemed ineligible per the 3-panel

The primary analysis will be repeated by including subjects randomized and received at least 1 dose of IP but deemed ineligible per the 3-panel consensus read i.e., subjects with fibrosis stage F1 or F4 or NAS < 4 at baseline per the 3-panel consensus read.

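### NASH resolution is scored as a Week 24 state, and the panel-based analysis set does not clearly exclude subjects already in that state at baseline, so an unchanged biopsy can count as a response on primary endpoint [a]

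*SAP*

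**What the plan says.** **Entry.** Protocol 5.1, criterion 3, asks for stage F2 or F3 and NAS of at least 4, "with a score of at least 1 in each of steatosis, ballooning degeneration, and lobular inflammation".

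**Analysis set.** SAP section 6 (and Protocol 9.3) defines the Full Analysis Set (FAS) by "confirmed fibrosis stage F2 or F3 and NAS ≥ 4 at baseline". The sentence continues "at baseline per independent review by a 3-pathologist panel who are eligible and assigned a randomization number in the study", without saying which criteria, or which biopsy read, the eligibility requirement refers to. The estimand population in SAP 7.8 uses the same stage and NAS limits, "per 3-panel consensus read who received at least 1 dose of IP", and has no eligibility wording. SAP 7.8.1 likewise restates only stage and NAS.

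**Who counts as ineligible.** SAP 7.8.1.2.3 adds back treated subjects "deemed ineligible per the 3-panel consensus read i.e., subjects with fibrosis stage F1 or F4" or with NAS below 4. A component score of zero is not listed.

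**Endpoint.** SAP 4.1.2 gives the rule: "Resolution of NASH includes the total absence of ballooning (score=0) and absent or mild inflammation (score 0 to 1"). SAP Table 2 adds only absence of fibrosis worsening for [a]. NAS has a range of 0 to 8, "which is the sum of Steatosis, Ballooning, and Lobular Inflammation".

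**Why entry and panel reads can differ.** Protocol 7.1.2 explains: "The initial protocol allowed subjects to be included based on the biopsy read by one of the 2 expert pathologists". Amendment 2 replaced this with a three-pathologist panel, and the re-read moved some subjects to another baseline fibrosis stage.

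**The concern.** A responder endpoint for resolution assumes that there is something to resolve. At entry, criterion 3 guarantees this, because ballooning must be at least 1. The analysis set was rebuilt on the panel read, and that guarantee was not carried over in terms. If the panel scores ballooning 0 and inflammation 0 or 1 in a subject whose entry reader saw ballooning, the subject starts in the responder state and needs only to stay there without fibrosis progression.

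For endpoint [a], baseline status would then be counted as treatment response. If such subjects are spread evenly over the arms, the difference from placebo is diluted. If they are not, the bias can go either way. Success is claimed for any dose on either primary endpoint at an unadjusted 0.05 (SAP 7.8 and 7.8.1), so an error in a single arm could matter.

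**Working it through.** **1. The plan's power figures.** Inputs from SAP 3.5: resolution 15% v 45%, fibrosis improvement 20% v 50%, 64 per group (40 for 44 mg Q2W), two-sided 0.05, 15% dropout. With n = 0.85 × 64 = 54.4 per arm,

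power = Φ{[Δ − 1.96 √(2p̄(1 − p̄)/n)] / √([p0(1 − p0) + p1(1 − p1)]/n)}.

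For resolution, p̄ = 0.30 and Δ = 0.30, so power = Φ[(0.300 − 0.172)/0.083] = 93.8% (stated 94%). Fibrosis improvement gives 91.8% (stated 92%). The unequal-n form for 44 mg (34 v 54.4) gives 87.1% and 84.0% (stated 87% and 83%). The plan's figures are reproduced to within about a point.

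**2. Which profiles are affected.** Steatosis 0–3, ballooning 0–2 and inflammation 0–3 give 4 × 3 × 4 = 48 profiles. Written in that order:
- 29 have NAS of at least 4.
- 12 of the 29 break the component minimum: six with ballooning 0 (103, 202, 203, 301, 302, 303), three with steatosis 0 (013, 022, 023) and three with inflammation 0 (220, 310, 320).
- Resolution needs ballooning 0 and inflammation of at most 1, which is 4 × 1 × 2 = 8 profiles. Their largest NAS is 3 + 0 + 1 = 4, so only 301 reaches the NAS limit.
- The other seven (000, 001, 100, 101, 200, 201, 300) have NAS below 4 and can enter only through SAP 7.8.1.2.3.
- With the component minimum applied to the panel read, 29 − 12 = 17 profiles remain and none meets resolution.

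**3. Which endpoints are affected by an unchanged 301 biopsy at F2 or F3.**
- [a] resolution, no fibrosis worsening: met.
- [b] fibrosis improvement of at least one stage: not met.
- [d] resolution and fibrosis improvement of at least one stage: not met. Only the resolution half is satisfied in advance.

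**4. Size.** The documents give no count. Assume a share f of each arm has the 301 profile and all of them count as responders. Then rate = p(1 − f) + f, and the difference is 30(1 − f) points.

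| f | Placebo | 30 mg QW | Difference (points) | Power, 30 mg |
|---|---|---|---|---|
| 0% | 15.0% | 45.0% | 30.0 | 93.8% |
| 1% | 15.85% | 45.55% | 29.7 | 93.0% |
| 2% | 16.7% | 46.1% | 29.4 | 92.2% |
| 5% | 19.25% | 47.75% | 28.5 | 89.4% |
| 10% | 23.5% | 50.5% | 27.0 | 84.0% |

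If only some stay in the responder state, at rates sA on active and sP on placebo, the difference is 30(1 − f) + 100f(sA − sP). Equal persistence gives the same differences as the table. With sA = 0.9 and sP = 0.6 it stays at 30 for every f.

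**5. Spread over the arms.** SAP 3.3 gives the initial allocation as 2:1:3:3:3, changed in April 2022 to 16:8:6:24:15. Subjects per pooled-placebo subject:

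| Arm | Initial | Later |
|---|---|---|
| 15 mg QW | 3/3 = 1.00 | 6/24 = 0.25 |
| 30 mg QW | 3/3 = 1.00 | 24/24 = 1.00 |
| 44 mg Q2W | 3/3 = 1.00 | 15/24 = 0.625 |

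Early subjects, who include those admitted on one read, are over-represented in the 15 mg and 44 mg arms relative to pooled placebo. If pre-met subjects are mostly early ones, their excess would favour those two arms on [a]. The 30 mg comparison is 1:1 in both periods, so dilution is the expected effect there. One subject in the planned 15 mg arm is 1/16 = 6.25 points.

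**The case against.** The strongest reply is that the FAS also requires subjects to be eligible. If that means all of criterion 3 on the panel read, the 301 subject is out of the FAS; and if it means only stage and NAS, the word adds nothing. This has force, and the text is ambiguous rather than plainly wrong. It does not close the gap. The estimand population has no such wording, and the SAP's own list of panel-ineligible subjects stops at stage and NAS. On the strict reading, a subject who fails only the component minimum would be in neither the FAS nor the 7.8.1.2.3 analysis, so that list would need correcting anyway. The endpoint's comparison with baseline (SAP 4.1.1) does not help either, because no rule says that resolution must have been absent.

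Second, the plan would make the problem visible. It tabulates baseline component scores by arm (SAP 7.4) and shifts in each component (7.8.1), adds randomization period as a stratification factor in a sensitivity analysis (7.8.1.2.2), and has an exploratory endpoint that adds a 2-point NAS improvement, which an unchanged biopsy cannot meet. All of this stands, but none of it changes how the primary analysis classifies the subject.

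Stronger readings that a reader might infer are not supported:
- *Key secondary [d] also counts baseline status as a response.* It does not, because it needs fibrosis improvement of at least one stage.
- *All 12 profiles that break criterion 3 are responders in advance.* Only one is. Profile counts are also not frequencies.
- *The 15 mg and 44 mg results will be inflated.* The allocation history makes an imbalance possible, but no document shows that any such subject exists.
- *The 7.8.1.2.3 analysis undermines the primary result.* It is a sensitivity analysis that adds ineligible subjects on purpose.

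**Conclusion.** The gap is real and narrow. As written, the plan does not prevent a 301 subject at F2 or F3 from counting as a responder on primary endpoint [a] with no histological change. Endpoint [b] is untouched, and [d] is touched only in its resolution half. The main route in is a single-reader entry before Amendment 2 that the panel later scored lower on ballooning. The 7.8.1.2.3 analysis is more exposed, since it opens the other seven profiles.

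The effect on the 30 mg comparison is probably small: 29.7 to 27.0 points instead of 30, and power of 93.0% to 84.0% instead of 93.8%, for an affected share of 1% to 10%. That range is an assumption, as are an equal share in both arms and every such subject being a responder. The plan gives nothing that supports the upper end for a single profile. For the 15 mg and 44 mg arms, neither the direction nor the size can be settled from the documents. The point is worth correcting because the stated rule gives a wrong classification and the correction is nearly free, not because a large bias has been shown.

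**What to change.** Before unblinding:

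1. In SAP 4.1.1, 4.1.2 and 7.8.1, and for the 7.8.1.2.3 analysis, count a subject as a resolution responder for [a], and for the resolution part of [d], only if resolution was not already present on the panel's baseline read, that is, panel baseline ballooning of at least 1 or inflammation of at least 2.
2. Report by arm how many subjects met resolution at baseline.
3. In SAP section 6, state whether the eligibility requirement applies criterion 3's component minimum on the panel read, and make the list in 7.8.1.2.3 match.

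Removing all 12 component-failing profiles from the FAS would also close the gap, but it excludes randomized subjects with 11 profiles that cannot be responders in advance, which is more than this error needs.

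The rule uses only the panel's baseline read, made blind to treatment and visit, and needs no new data. Protocol section 9 gives the SAP precedence, so a SAP change is enough. The cost is a slightly lower response rate in any arm that contains such subjects.

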7.8.1.2.4. Treating subjects with missing histology endpoint as non-responders

The primary analysis will be carried out by imputing a subject with missing histology endpoint as a non-responder for the endpoint.

7.8.1.3. Subgroup Analysis

The primary analyses and the completer analysis will be repeated in the subgroups, as noted in Section 4.3.

The point estimates and 95% confidence interval (CI) for the differences in proportions will be calculated for each subgroup and visualized via forest plots for primary endpoints.

7.8.2. Secondary Efficacy Analysis

The planned primary and completer analysis for the primary endpoints will be repeated for the key secondary endpoints. Subgroup analysis will be repeated for proportion of patients with NASH resolution and fibrosis improvement ≥ 1 stage at Week 24 compared to baseline.

MRI-PDFF will be analyzed based on MRI-PDFF Analysis Set. All other secondary efficacy analyses will be analyzed based on the Full Analysis Set with confirmed fibrosis stage F2 or F3 and NAS ≥ 4 at baseline per 3-panel consensus read. For hepatic fat fraction by MRI-PDFF, ALT, Pro-C3, adiponectin, serum triglycerides, HDL-c, Non-HDL-c, LDL-c and HbA1c, absolute values, changes, and percentage changes at baseline and each scheduled post-baseline visits will be summarized. Change and percentage change from baseline to post-baseline visits

will be analyzed by a mixed model repeated measures (MMRM) method (use ANCOVA for single post-baseline measurement) with treatment group, visit week, and treatment-by-week interactions as main effects, baseline measurement and two stratification factors as covariates in the model. An unstructured covariance matrix will be used to represent the correlation of the repeated measures within each subject whenever the model converges. The model will provide the least square (LS) mean, SE and 2-sided 95% CI for mean change or percent change from baseline within and between treatments. P-values will be calculated to compare the treatment effect in each pegozafermin group to that in the placebo group at specific study weeks. Each treatment group comparison will be performed at a 2-sided 0.05 significance level.

Changes and percentage changes from baseline to post-baseline visit will be visualized via line plots.

If the mixed or ANCOVA model assumption of the MMRM method is severely violated, the non-parametric van Elteren test stratified by T2DM status (yes vs. no) and fibrosis stage (F2 vs. F3) will be performed. The location shift estimate, and Hodges-Lehmann 2-tailed 95% confidence interval will be presented. For the comparison between the individual dose group and the placebo, if small cell counts (<5) render the van Elteren test inappropriate, the un-stratified Wilcoxon rank-sum test will be used instead.

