In addition to the primary analysis, standard sensitivity analyses, namely, sensitivity analyses based on the hypothetical (missingness at random) strategy, return-to-baseline imputation and control-based imputation, will be conducted. The details of these analyses are presented in Table 5. In all cases, a multiple imputation approach will be applied and imputation models will be based on a Bayesian logistic regression model with subject baseline fibrosis stage, diabetes status, age, gender and baseline NAS score included in the model. The estimated effects and associated standard errors from the individual completed data sets will be combined using Rubin's rules to produce a single inferential statement (treatment effect, standard error and p-value).

Table 5: Primary and sensitivity analyses for three types of ICEs

Analysis	ICE-1	ICE-2	ICE-3
Primary analysis	Use all collected outcomes regardless of ICEs. Impute missing outcomes based on an imputation model informed by the relevant baseline data and type of ICE (“none”,1,2,3). If most subjects with ICE have missing outcomes, type of ICE covariate will be removed from the imputation model.		
Sensitivity analysis by ICE type	Set all post-baseline outcomes as missing. Impute missing outcomes based on an imputation model informed by the baseline data alone (return-to-baseline).	Set all outcomes following ICE as missing. Impute missing outcomes based on an imputation model informed by patients who did not have any of the three ICEs using only the data from the placebo arm.	Set all outcomes following ICE as missing. Impute missing outcomes based on an imputation model informed by patients who did not have any of the three ICEs using only the data from the treatment arms.

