7.8.1.1. Primary analysis

The primary analysis will be carried out using an MI-based strategy that includes the following three steps:

- Step 1. Missing outcomes will be imputed a large number of times ($M=100$) using PROC MI based on the model outlined in Table 5 based on a logistic regression model.
- Step 2. The Cochran-Mantel-Haenszel (CMH) test stratified by T2DM status (yes vs. no) and fibrosis stage (F2 vs. F3) will be applied to each completed data set to compare the proportions of responders at Week 24 between each pegozafermin group and placebo, adjusting for the stratification factors. The point estimates and associated standard errors for the differences in proportions as well as CMH test statistics will be calculated.
- Step 3. The CMH summaries from individual completed sets will be combined using Rubin’s rules to produce a single inferential statement (treatment effect, standard error, 95% confidence interval and p-value) via PROC MIANALYZE.

Note that a patient can have only one ICE (classified as ICE-1, -2, -3) or none (0). Once an ICE of specific type has occurred, the status of ICE variables remains fixed at that value until the end of the trial. All collected data are used in imputation. Imputation is done by the trial arm (TRT) but, if the data are sparse, instead of imputing by TRT, include TRT as covariate.

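### Key secondary endpoint [e] combines biopsy, MRI-PDFF and ALT, but the SAP has no rule for subjects with only some components observed, and its imputation model uses neither MRI-PDFF nor ALT

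*SAP*

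**What the plan says.** SAP 4.1.2 defines [e] as a NAS gain of two points or more in subjects who "AND are MRI-PDFF responders⁵ AND ALT responders⁶ at Week 24 compared to baseline". Table 2 there marks all three criteria as required, so failing any one settles the outcome.

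For the analysis, SAP 7.8.2 states: "The planned primary and completer analysis for the primary endpoints will be repeated for the key secondary endpoints". It adds nothing specific to [e]. The method carried over is as follows:

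- **What is imputed** (7.8.1.1): "Missing outcomes will be imputed a large number of times", with 100 imputations by logistic regression, followed by stratified CMH and Rubin's rules.
- **Predictors** (7.8.1): a "Bayesian logistic regression model with subject baseline fibrosis stage, diabetes status, age, gender and baseline NAS score included in the model". SAP 7.8 adds randomized arm and intercurrent-event (ICE) type.
- **Table 5, primary row**: "Use all collected outcomes regardless of ICEs", and then "Impute missing outcomes based on an imputation model informed by the relevant baseline data and type of ICE". ICE type is dropped if most subjects with an ICE have missing outcomes.

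Neither baseline nor Week 24 MRI-PDFF or ALT is a listed predictor. The SAP does not say when [e] counts as missing, or whether its components are imputed separately.

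**The concern.** The method was written for the primary endpoints, whose elements all come from one biopsy and go missing together. Endpoint [e] is the only primary or key secondary endpoint built from three separate assessments. A subject can have Week 24 MRI-PDFF and ALT but no readable biopsy, or a biopsy that fails on NAS with MRI or ALT missing.

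The text leaves two ways to proceed, and both have a fault.

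1. **Impute [e] whenever any component is missing.** Subjects whose observed data already rule out response then receive a positive probability of response. This sets aside collected outcomes, contrary to Table 5.
2. **Code known failures as 0 and run the same model on the rest.** Many of the subjects left to impute have already passed MRI-PDFF and ALT, yet they are imputed at the arm's average rate.

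Two analysts following the SAP could therefore report different results for [e].

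**Working it through.** **The plan's own figures.** The SAP gives no rate, sample size or power for [e]. Its primary-endpoint powers (SAP 3.5) reproduce with a pooled-variance two-proportion test, two-sided 0.05, after removing 15% for dropout (54.4 per arm; 54.4 vs 34):

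| Comparison | Stated | Recomputed |
|---|---|---|
| 30 mg QW, NASH resolution | 94% | 93.8% |
| 30 mg QW, fibrosis | 92% | 91.8% |
| 44 mg Q2W, NASH resolution | 87% | 87.1% |
| 44 mg Q2W, fibrosis | 83% | 84.0% |

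So 15% is the plan's working dropout figure. It is used below as an upper value for missing biopsies.

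**Inputs.** From the SAP: m = 0.15 and 64 per arm. Assumed: completer [e] rates r1 = 45% and r0 = 15%, borrowed from the NASH-resolution assumptions. Also assumed: s, the share of non-biopsied subjects with Week 24 MRI/ALT; k, their joint MRI+ALT response relative to completers; q, the joint MRI+ALT response rate; and a, the NAS response rate among those who pass both.

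**Reading 1, whole-endpoint imputation.** Non-biopsied subjects are imputed at about r. If NAS response given MRI+ALT response is the same as in completers, the true rate is k × r among those with MRI/ALT. The part of the bias that observed MRI/ALT could remove is m × s × (1 − k) × r per arm, and m × s × (1 − k) × (r1 − r0) in the difference.

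| k, both arms, s = 1 | Bias in the difference |
|---|---|
| 1 | 0 |
| 1/2 | 0.15 × 1/2 × 0.30 = 2.3 points |
| 1/3 | 0.15 × 2/3 × 0.30 = 3.0 points |
| 1/5 | 0.15 × 4/5 × 0.30 = 3.6 points |

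- With s = 0.5 these halve to 1.1, 1.5 and 1.8 points.
- Only active-arm subjects fall short: 0.15 × 1/2 × 0.45 = +3.4 points, or 0.15 × 2/3 × 0.45 = +4.5 points.
- Only placebo subjects fall short: 0.15 × 1/2 × 0.15 = 1.1 points, or 0.15 × 2/3 × 0.15 = 1.5 points, in the opposite direction.

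Expected responders imputed among known failures, per 64 active subjects, are 64 × 0.15 × s × (1 − joint response in the non-biopsied) × 0.45. With joint response 0.30 and s = 0.5 this is 1.5. With 0.15 and s = 1 it is 3.7.

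**Reading 2, known failures coded 0, random missingness.** The model is fitted to completers plus known failures, so its rate is (1 − m) × q × a / [(1 − m) + m × s × (1 − q)]. Everyone left is imputed at that rate, so it is also the arm estimate. Active arm with q = 0.6 and a = 0.75, true rate 45.0%:

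- s = 1: 0.3825 / (0.85 + 0.06) = 42.0%
- s = 0.5: 0.3825 / (0.85 + 0.03) = 43.5%

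Placebo with q = 0.15 and a = 0.5, true rate 7.5%:

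- s = 1: 0.06375 / 0.9775 = 6.5%
- s = 0.5: 0.06375 / 0.91375 = 7.0%

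The true difference of 37.5 points becomes 35.5 or 36.5, understated by about 5% or 3%. With q = 0.7, a = 0.65 against q = 0.3, a = 0.5, the true 30.5 points becomes 29.9 (s = 1) or 30.2 (s = 0.5), understated by about 2% or 1%.

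**Component imputation, same case.** With s = 1, known failures contribute 0 and those who passed are imputed at a: 0.3825 + 0.15 × 0.6 × 0.75 = 45.0%, the true rate.

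**The case against.** A reader might infer that the SAP orders [e] to be imputed as a whole from baseline data, and that the effect is therefore inflated. The documents do not support that. No sentence says the composite is imputed as a whole. Table 2 fits equally well with treating an observed failure as a settled non-response, and 7.8.1.1 has a general remark that all collected data enter the imputation. The model is not baseline-only, since it includes arm and ICE type. An impossible value for one subject does not by itself bias the arm rate.

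The affected group is also limited. Protocol 7.1 restricts visits after IP discontinuation to AEs and concomitant medications, and asks for a biopsy at the early-termination visit from Week 16 to before Week 24. Under SAP 6.2 the Week 24 window opens at Day 142 for ALT. For MRI-PDFF it opens just after the Day 85 to Day 169 midpoint, Day 127. Both fall after Week 16 (Day 113), so an early-termination visit that supplies Week 24 MRI/ALT is generally one where a biopsy is also requested. The group is then mainly those who decline the biopsy or have an unreadable one: an unknown and probably small part of the 15%.

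Finally, trial success rests on the two primary endpoints, there is no multiplicity adjustment, and 3.6 points is less than half the standard error of the difference, √[(0.45 × 0.55 + 0.15 × 0.85)/54.4] = 8.3 points.

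All of this limits the size of the point. It does not supply the missing rule. The general remark names no component and does not fit the listed predictors. The settled-non-response reading still needs a different model, as Reading 2 shows. The planned completer analysis requires biopsies only, so MRI or ALT can still be missing in it. The non-responder analysis (7.8.1.2.4) is not among those repeated for [e].

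**Conclusion.** The point stands as a gap in specification with a cheap, better method available. The SAP carries a single-assessment imputation over to a three-assessment composite, with no rule for partly observed cases and with neither MRI-PDFF nor ALT in the model.

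The size depends on assumptions the documents cannot settle. Under the literal reading the bias is zero when missing biopsy is unrelated to MRI/ALT response. It is about 2 to 4 points at the full 15% with k between 1/2 and 1/5 in both arms, proportionally less with smaller s, and of either sign if one arm is affected. Under the alternative coding, the active rate falls from 45.0% to 42.0 to 43.5% in the worked example even under random missingness. A claim that the effect on [e] is overstated would go beyond the documents.

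A reader might also extend the point to exploratory composites [7] to [11]. SAP 7.8.3 clearly carries over only the CMH method for these, so the point applies to them only if they are multiply imputed.

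**What to change.** In SAP 7.8.2, add a rule for [e]:

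1. [e] is non-response whenever any observed Week 24 component fails.
2. Otherwise impute only the missing component or components, conditional on the observed components, baseline MRI-PDFF and ALT, and the existing covariates. Treatment enters as a covariate where arms are sparse, which 7.8.1.1 already permits.
3. Derive [e] in each of the 100 completed data sets, then apply CMH and Rubin's rules as planned.

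Apply the same rule to [7] to [11] only if they are multiply imputed.

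The cost is a few lines of text and a fully conditional specification statement in PROC MI, with no new data. The downside is more terms in the imputation model, with possible separation in the 15 mg arm (planned N = 16) if the model is fitted by arm.
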